Analyses for the secondary endpoints will be done using observed data and no imputation will be used for missing observation.

All details regarding the statistical analyses will be included in a separate statistical analysis plan.

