3.4.2.2 Secondary Efficacy Variable

Secondary efficacy variables are as follows:

- The **Eczema Area and Severity Index (EASI)** will be assessed at each visit, except screening visit. It quantifies the severity of a subject's atopic dermatitis based on both lesion severity and the percent of BSA affected.

Four anatomic sites – head, upper extremities, trunk, and lower extremities – are assessed for erythema, induration (papules), excoriation and lichenification as seen on the day of the examination. The severity of each sign is assessed using a 4-point scale: 0 = No symptoms, 1 = Slight, 2 = Moderate, 3 = Marked.

The area affected by atopic dermatitis within a given anatomic site is estimated as a percentage of the total area of that anatomic site and assigned a numerical value according to the degree of atopic dermatitis involvement as follows: 0 = no involvement, 1 = < 10 %, 2 = 10 to < 30%, 3 = 30 to < 50%, 4 = 50 to < 70%, 5 = 70 to < 90%, 6 = 90 to 100 %.

The EASI score is obtained by using the formula:

$$\begin{aligned} \text{EASI} = & 0.1 * (E_h + I_h + Ex_h + L_h) * A_h + \\ & 0.2 * (E_u + I_u + Ex_u + Ex_u) * A_u + \\ & 0.3 * (E_t + I_t + Ex_t + Ex_t) * A_t + \\ & 0.4 * (E_l + I_l + Ex_l + Ex_l) * A_l \end{aligned}$$

Where E, I, Ex, L and A denote erythema, induration, excoriation, lichenification and area, respectively, and h, u, t, and l denote head, upper extremities, trunk, and lower extremities, respectively. The EASI score ranges from 0 (no disease) - 72 (maximal disease). The score will be set to missing in case of at least one missing value.

The change from baseline in EASI at Week 2, Week 4, Week 8, and Week 10 will be calculated as the value at the visit minus the value at Baseline. Percent change from baseline will also be calculated. In addition, change and percent change from Week 8 to Week 10 will be calculated.

- The overall **Body Surface Area (BSA)** affected by AD will be evaluated (from 0 to 100%) at each visit. One patient's palm represents 1% of his/her total BSA. For all study visits except at screening, the BSA of involved skin will be measured with the SCORAD measurement. The change from Baseline will be calculated as the value at the visit minus the value at Baseline. The change from baseline will be calculated at Week 2, Week 4, Week 8 and Week 10. Percent change from baseline will also be calculated. In addition, change and percent change from Week 8 to Week 10 will be calculated.

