- The **SCORing Atopic Dermatitis (SCORAD)** will be measured at each visit, except the screening visit. The SCORAD grading system is a standard tool to assess the AD severity in clinical studies in Europe. Six items (erythema, edema/papulation, oozing/crusts, excoriation, lichenification, and dryness) are selected to evaluate the AD severity. The intensity of each item is graded using a 4-point scale: 0 = No symptoms, 1 = Mild, 2 = Moderate, 3 = Severe.

The area chosen for grading must be representative (average intensity) for each item. The individual intensity ratings for each item will then be added (ranging from 0-18) and multiplied by 3.5, giving a maximal score of 63.

The overall BSA affected by AD is evaluated (from 0 to 100%) and divided by 5. One patient's palm represents 1% of his/her total BSA. The maximum is 20.

Subjective items include loss of sleep and the occurrence of pruritus. These are evaluated by asking patients to indicate on the 10-cm scale (0-10) of the assessment form the point corresponding to the average value for the last three days/nights. The combined maximum score of these two is 20.

The sum of the above measures represents the SCORAD which can vary from 0 to 103. If the subjective scores of pruritus and loss of sleep are excluded, the SCORAD becomes objective SCORAD (score range 0-83).

The score will be set to missing if there is at least one missing value. The change from Baseline will be calculated as the value at the visit minus the value at Baseline. The change from baseline will be calculated at Week 2, Week 4, Week 8, and Week 10. Percent change from baseline will also be calculated. In addition, change and percent change from Week 8 to Week 10 will be calculated.

- The **Visual Analog Scale (VAS) of Pruritus** will be assessed with the SCORAD measurement for all study visits except screening. This will be evaluated by asking subjects to indicate on the 10-cm scale (0-10) of the assessment form the point corresponding to the average value for the last three days/nights. The change from Baseline will be calculated as the value at the visit minus the value at Baseline. The change from baseline will be calculated at Week 2, Week 4, Week 8, and Week 10. Percent change from baseline will also be calculated. In addition, change and percent change from Week 8 to Week 10 will be calculated.

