- The **Patient-Oriented Eczema Measure (POEM)** will be assessed at each visit, except screening visit. The POEM is a self assessment of disease severity by the patient. The following questions are to be rated as: 0=No Days, 1=1-2 Days, 2=3-4 Days, 3=5-6 Days, 4=Everyday.

1. Over the last week, on how many days has your skin been itchy because of your eczema?
2. Over the last week, on how many nights has your sleep been disturbed because of your eczema?
3. Over the last week, on how many days has your skin been bleeding because of your eczema?
4. Over the last week, on how many days has your skin been weeping or oozing clear fluid because of your eczema?
5. Over the last week, on how many days has your skin been cracked because of your eczema?
6. Over the last week, on how many days has your skin been flaking off because of your eczema?
7. Over the last week, on how many days has your skin felt dry or rough because of your eczema?

The POEM score is the sum of the 7 question ratings for a possible total of 28 (more severe eczema). The score will be set to missing if there is at least one missing value. The change from Baseline will be calculated as the value at the visit minus the value at Baseline. The change from baseline will be calculated at Week 2, Week 4, Week 8, and Week 10. Percent change from baseline will also be calculated. In addition, change and percent change from Week 8 to Week 10 will be calculated

- The **Dermatology Life Quality Index (DLQI)** questionnaire is a simple 10-question validated questionnaire which will be completed at each visit, except screening. The following questions are to be assessed by the patient:

1.	Over the last week, how itchy, sore, painful or stinging has your skin been?	Very much (3) A lot (2) A little (1) Not at all (0)	
2.	Over the last week, how embarrassed or self conscious have you been because of your skin?	Very much (3) A lot (2) A little (1) Not at all (0)	
3.	Over the last week, how much has your skin interfered with you going shopping or looking after your home or yard ?	Very much (3) A lot (2) A little (1) Not at all	Not relevant (0)
4.	Over the last week, how much has your skin influenced the clothes you wear?	Very much (3) A lot (2) A little (1)	

		Not at all	Not relevant (0)
5.	Over the last week, how much has your skin affected any social or leisure activities?	Very much (3) A lot (2) A little (1) Not at all	Not relevant (0)

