6.	Over the last week, how much has your skin made it difficult for you to do any sport ?	Very much (3) A lot (2) A little (1) Not at all	Not relevant (0)
7.	Over the last week, has your skin prevented you from working or studying ?	Yes (3) No (0)	
	If "No", over the last week how much has your skin been a problem at work or studying ?	A lot (2) A little (1) Not at all (0)	
8.	Over the last week, how much has your skin created problems with your partner or any of your close friends or relatives ?	Very much (3) A lot (2) A little (1) Not at all	Not relevant (0)
9.	Over the last week, how much has your skin caused any sexual difficulties ?	Very much (3) A lot (2) A little (1) Not at all	Not relevant (0)
10.	Over the last week, how much of a problem has the treatment for your skin been, for example by making your home messy, or by taking up time?	Very much (3) A lot (2) A little (1) Not at all	Not relevant (0)

The DLQI score is the sum of the 10 questions for a possible total of 30 (quality of life is impaired). 'Not relevant' and 'Unanswered' questions will be scored as 0. The change from Baseline will be calculated as the value at the visit minus the value at Baseline. The change from baseline will be calculated at Week 2, Week 4, Week 8, and Week 10. Percent change from baseline will also be calculated. In addition, change and percent change from Week 8 to Week 10 will be calculated

- **Trans epidemal Water Loss (TEWL)**, the clinical severity of AD and associated effect on skin barrier function will be evaluated at each visit, except the screening visit. This evaluation will be performed at selected sites that have demonstrated previous experience with this device.

At Baseline (Day 0), the investigator will select three representative areas of active AD for each subject; the location of these sites will be recorded. At subsequent visits, TEWL readings for each area of AD will be taken in standard room ambient conditions (22-25°C, 40-60% relative humidity); the mean of the TEWL measurements will be used for the

analyses. The change from Baseline will be calculated as the value at the visit minus the value at Baseline. The change from baseline will be calculated at Week 2, Week 4, Week 8, and Week 10. Percent change from baseline will also be calculated. In addition, change and percent change from Week 8 to Week 10 will be calculated.

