5.3 Missing Data/Multiple Observations

No imputation will be done for all population and all parameters, except for the primary endpoint. A supportive analysis using the last observation carried forward (LOCF) method will be performed on responder analysis (see section 7.1 for details).

In the event that two values were collected for the same visit, the scheduled assessment value will be retained in the analyses, unless otherwise specified (e.g. lab error). However, all values will be presented in the data listings. Laboratory values of '< X' or '> X' will be set to 'X' for the analysis.

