7.2 Secondary Efficacy Analyses

The second efficacy endpoints are:

- Change from baseline in IGA at week 2, 4, and 8
- Change from baseline in EASI at week 2, 4, and 8
- Change from baseline in POEM at week 2, 4, and 8
- Change from baseline in DLQI at week 2, 4, and 8
- Change from baseline in SCORAD at week 2, 4, and 8
- Change from baseline in VAS at week 2, 4, and 8
- Change from baseline in BSA at week 2, 4, and 8
- Proportion of patients achieving at least 1-point decrease in IGA at Week 8

All secondary endpoint based on the change from baseline will be assessed using an ANCOVA where the change from baseline will be the dependant variable and including the treatment group and site as fixed effects and baseline value as a covariate. In addition, ANCOVA will also be performed on the change from baseline at week 10 and on the change from Week 8 to Week 10.

All secondary endpoint based on categories will be analysed using a Cochran-Mantel-Haenszel test stratified by site and the p-value from this test will be presented along with frequency and percentage of subjects for each category.

All change and percent change values will be summarized using descriptive statistics, for each treatment group and visit. Proportion of subjects with no, 1-point, 2-point, 3-point, decrease/increase, will be presented at Week 8.

All statistical analyses will be done at each visit and using the ITT (primary analysis) and PP (supportive analysis) population. All the analyses will be done using observed values. Results collected during the early termination visit related to Week 8 and Week 10 will not be included. No sensitivity analysis will be done for missing values.

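### DLQI items left blank are scored 0, the best category, with no limit on blanks, so an incomplete form gives a total that can only equal or understate the true one

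*SAP*

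**What the plan says.** SAP 3.4.2.2 defines the DLQI total as the sum of 10 items with a maximum of 30, higher meaning worse quality of life. The response key runs "Very much (3) A lot (2) A little (1) Not at all (0"), so 0 is the best answer. The rule for incomplete forms is that "Not relevant' and 'Unanswered' questions will be scored as 0". No maximum number of blanks is given, and nothing says when the total becomes missing.

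The same section treats the other composite scores differently. For EASI, "The score will be set to missing in case of at least one missing value". For SCORAD and POEM, "The score will be set to missing if there is at least one missing value".

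The general missing-data statements are:

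- Protocol 14.2.2: "Analyses for the secondary endpoints will be done using observed data and no imputation will be used for missing observation".
- SAP 5.3: "No imputation will be done for all population and all parameters, except for the primary endpoint".
- SAP 7.2, on the secondary endpoints: "All the analyses will be done using observed values" and "No sensitivity analysis will be done for missing values".

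Change from baseline in DLQI at Weeks 2, 4 and 8 is a secondary endpoint, tested by ANCOVA (SAP 7.2).

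**The concern.** The rule turns non-response into a report of no impairment. A blank cannot simply be read as 'does not apply'. On the form in Protocol Appendix F, items 3 to 10 carry their own 'Not relevant' box, items 1 and 2 offer none, and the patient is asked to check that nothing has been skipped. Scoring 'Not relevant' as 0 is a separate matter and is not questioned here, because it is an answer the patient chose.

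Assigning a value to an unanswered item is imputation at item level. SAP 5.3 excepts only the primary endpoint and does not mention the DLQI.

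For change from baseline the error can run either way: a blank after baseline looks like improvement and a blank at baseline looks like worsening. If blanks were more frequent in one arm, the treatment comparison would shift toward that arm after baseline. With no sensitivity analysis planned for missing values in the secondary endpoints, nothing in the analysis would show it.

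**Working it through.** **Inputs from the documents.** Ten items, each 0 to 3. Item 7 also tops out at 3: 'Yes' scores 3, and 'No' scores 0 plus a follow-up of at most 2. The sample-size sections (Protocol 14.1, SAP 4) give 45 subjects, 10% drop-out and 100 in total. I read 45 as per arm because 2 × 45 / 0.9 = 100.

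**Stated maximum.** 10 × 3 = 30, as the SAP says.

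**Effect of k blanks on one form.** Each blank replaces a true value of 0 to 3 by 0. Scored minus true therefore lies between −3k and 0, and the highest attainable total is 30 − 3k.

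| Blanks k | Scored minus true | Highest attainable total |
|---|---|---|
| 1 | −3 to 0 | 27 |
| 2 | −6 to 0 | 24 |
| 5 | −15 to 0 | 15 |
| 10 | −30 to 0 | 0 |

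**Assumptions for the expected size.** The documents give no blank rate and no DLQI mean. I assume a blank rate q of 1% to 3% per item, independent across items, and a true total T of 12 (range 6 to 18).

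- Mean understatement of a visit total, T × q: 12 × 0.01 = 0.12 to 12 × 0.03 = 0.36 points. Over T = 6 to 18 the range is 0.06 to 0.54.
- Equal q in both arms: the expected total is (1 − q) times the true total, so the arm difference shrinks by 1-3%.
- Post-baseline blanks of 1% in one arm and 3% in the other: shift in the arm difference T × 0.02 = 0.24 points (0.12 to 0.36 for T = 6 to 18).
- A patient stable at 12 (average 1.2 per item): one blank at Week 8 gives a false change averaging −1.2, five blanks −6, a wholly blank form −12 (−100%).
- One wholly blank Week 8 form among 45 in an arm: 12/45 = 0.27 points on that arm's mean change (6/45 = 0.13 to 18/45 = 0.40; at most 30/45 = 0.67).

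**What a limit on blanks would do at the same rates.**

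| Quantity | Formula | q = 1% | q = 2% | q = 3% |
|---|---|---|---|---|
| Forms with any blank | 1 − (1 − q)^10 | 9.6% | 18.3% | 26.3% |
| Forms with two or more blanks | 1 − P(0) − P(1) | 0.43% | 1.62% | 3.45% |
| Changes lost, limit at two blanks | 1 − (1 − P(≥2))² | 0.85% | 3.2% | 6.8% |
| Changes lost, any blank makes the total missing | 1 − (1 − q)^20 | 18.2% | 33.2% | 45.6% |
| Mean understatement left, limit at two (T = 12) | 1.2 × P(1) / (P(0) + P(1)) | 0.11 | 0.20 | 0.28 |

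**The case against.** The best defence is that this is an explicit, prespecified scoring rule for one instrument. A specific rule can be read alongside a general no-imputation statement, and a programmer would know what to do. That is fair for a single blank, where the gap is mainly the missing cross-reference in SAP 5.3. It does not justify leaving the number of blanks unlimited, nor does it separate a form with no answers from one not done. A wholly blank form might well be treated as missing in practice, but the text does not say so.

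Next, the effect is small, and in a double-blind trial there is no evident reason for blanks to differ by arm. That stands: the 1% against 3% case is hypothetical, and every expected size rests on assumed rates, independence and means. A limit at two blanks also changes the average error little, from 0.12-0.36 to 0.11-0.28 points. Its value lies in bounding the error on a single form.

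Different instruments may have different rules. EASI is clinician-rated and SCORAD largely so. POEM, however, is completed by the patient, and its form (Protocol Appendix E) invites blanks; yet one blank voids its total, while the DLQI form asks for every answer and accepts any number of blanks.

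Finally, the item 7 follow-up is properly empty after 'Yes' or 'Not relevant', and the SAP key for item 7 omits the 'Not relevant' option that the protocol form offers. This is a fair point for the wording of the fix; it does not rescue the rule for the other items.

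**Conclusion.** The concern holds. As written, the rule gives totals that are too low whenever an unanswered item would truly have scored above 0, and nothing limits how far. This much follows from the documents alone. Under the stated assumptions the average effect is minor, a few tenths of a point on a 30-point scale, and equal blank rates dilute the treatment difference slightly without favouring an arm. The practical risk is the occasional heavily incomplete form that enters the ANCOVA as a large improvement or, at baseline, as a worsening. Only one secondary endpoint is involved. It should be corrected because the correction is cheap.

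**What to change.** In SAP 3.4.2.2, before database lock:

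- keep 'Not relevant' at 0;
- set the DLQI total to missing when two or more of the 10 items are unanswered;
- count item 7 and its follow-up as one item, so that a follow-up skipped after 'Yes' or 'Not relevant' is not a blank, and state how 'No' with an empty follow-up is counted.

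In SAP 5.3, name the single blank scored 0 as an exception to the no-imputation rule.

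This takes a few sentences and a small programming change. No new table is needed, since Listing 16.2.6.4 already shows the items by treatment group. The threshold of two is a judgement, not a figure from the documents. It bounds the error at 3 points per form instead of 30 and, at the assumed rates, keeps 96.5-99.6% of forms. The cost is 0.9-6.8% of changes from baseline, which are not recovered because no imputation is planned. Making the total missing with any blank would match EASI, SCORAD and POEM but could lose 18-46% of changes (fewer if the same patients leave the blanks), so I do not recommend it.

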3.4.3 Safety Variables

3.4.3.1 Adverse Events

Treatment-emergent adverse events (TEAEs) are defined as AEs that developed, worsened or became serious after the first dose of study drug during the study, i.e. from the study drug start date to the end of study.

TEAEs will be coded according to Medical Dictionary for Regulatory Activities (MedDRA, version 17.0) terminology. The coding process using MedDRA will be conducted by the data management where lower level term (LLT), the preferred term (PT) and system organ class (SOC) will be assigned to each AE term.

Descriptions of AEs will include the date of onset, the date the AE ended (if it resolved), the severity and seriousness of the AE, the relationship of the AE to study medication, and the outcome. If the onset date of the AE is incomplete or missing and the end date is incomplete or missing, or the end date is after the start of treatment, then the event will be evaluated as a TEAE. If the start date is at the Baseline Visit and the end date is incomplete or missing, then the event will be evaluated as a TEAE. The AE onset will also be shown relative (in number of days) to the day of first dose.

3.4.3.2 Laboratory Safety Variables

Urinalysis, hematology (with differential and coagulation testing), a standard chemistry panel (chemistry includes liver function tests and cholesterol), coagulation, and serum pregnancy test for women of childbearing potential will be collected during the study (see Figure 1. Study Flow Chart for details). The list of laboratory parameters are presented in Table 1 below.

Table 1. Clinical laboratory Testing

Laboratory testing	Tests included
Hematology	Basophils, Eosinophils, HCT, HGB, Lymphocytes, MCH, MCV, Monocytes, Neutrophils, platelets, RBC, WBC
Coagulation	APTT, INR, PT
Serum Chemistry	Albumin, Alkaline Phosphatase, ALT, AST, Chloride, Cholesterol (non-fasting), CK, Creatinine (Enzymatic), GGT, Glucose Random, LDH, Potassium, Sodium, Total Bilirubin, Triglycerides, Urea (BUN), Uric Acid β-hCG for females of childbearing potential
Urinalysis	Blood, Glucose, pH, Protein

Laboratory results will be transferred by the laboratory itself. The data will include the visit date and time, the laboratory result type (e.g. hematology), the analyte name, the result, the unit, the reference values, and the abnormal flag.

3.4.3.3 Vital Signs

Vital signs will be assessed at each visit and include systolic and diastolic blood pressure, pulse, oral temperature and respiratory rate. The following variables were created for each vital sign.

- Value at the time specified is the value specified for the parameter on the CRF
- Change from baseline is the value at the time specified minus the value at baseline

3.4.3.4 Physical Examination

The following sites/systems will be included in the Physical examination. Each system will be scored as: Normal, Abnormal Not Clinically Significant, or abnormal clinically significant.

- General appearance
- Dermatological (except atopic dermatitis)
- Head, Eyes, Ears, Nose, Throat (HEENT)

- Respiratory
- Cardiovascular
- Abdominal
- Neurological
- Musculoskeletal
- Lymphatic

3.4.3.5 Total and Free DGLA plasma levels, Total Fatty Profile and Interleukins levels

Total DGLA and free DGLA trough plasma levels will be measured at Baseline, week 4 and week 8. Total fatty profiles and interleukins levels will not be covered in this SAP.

4 Sample Size

The primary endpoint can be translated as a responder analysis where a subject will be classified as Responder if he/she achieves an IGA score of 0 (clear) or 1 (almost clear) at Week 8, considering a 2-point decrease from baseline. A sample size of 45 subjects will have a power of 80% to detect a statistically significant difference of 25% between responders from treated group and from the placebo group, based on a chi-square test and an alpha of 0.05. Based on the literature review, it is expected that the placebo could reach up to 7%, so the minimal proportion expected in the treated group should be at least 32%. Allowing for 10% drop-out, a total of 100 subjects should be enrolled in the study.

5 General Considerations

